Urinary dysfunction includes frequency, incontinence, frequent infections, occurs in about 80-90% of MS patients. It causes a major disruption in daily life, imposing economic burdens for patients and their families. Direct costs and indirect costs as psychological distress, loss of productivity are a significant burden for the patient, and increase the risk of unemployment.(Moore, 2001) Besides interfering with quality of life, urinary dysfunctions leads commonly to urinary tract infections which can have a direct impact on MS, worsening neurologic symptoms, and increasing in the number of relapses, which may lead to disability.

Estriol for urogenital health

Urinary dysfunction is frequently treated with antimuscarinic agents; side effects from these drugs (dry mouth, blurred vision, constipation and difficulty with micturition) make compliance an issue (David et.al). Transvaginal estriol decreases urinary symptoms and prevents urinary tract infections.(Rahn et al., 2014) There is less risk of endometrial hyperplasia and endometrial cancer with estriol treatment compared with estradiol treatment (Cody, Jacobs, Richardson, Moehrer, & Hextall, 2012). Furthermore, vaginal delivery offers regional benefits to the lower urogenital tract, it is well absorbed and it is not associated with entero-hepatic recirculation as oral estriol, as some of the adverse effects of oral estrogens are to produce an increase in thromboembolic events. (Rahn et al., 2014)

Estriol in MS, role in remyelination

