Oral estriol has been shown to produce a significant decrease in the relapse rate in MS patients(Voskuhl et al., 2016). One of the reasons why vaginal estriol has a better absorption is that oral estriol is associated with entero-hepatic recirculation, which prolongs exposure due to recycling. Furthermore, vaginal estrogen delivery has a regional benefit to the lower urogenital tract, and is well absorbed at a dose of 0.5 mg to 1 mg. In a systematic review of randomized trials comparing vaginal estrogens, it was concluded that the 1mg vaginal estriol, was superior to lower doses for the treatment of urogenital symptoms. (Rahn et al., 2014) In animal models, estriol demonstrated to have distinctly different modulatory actions on the immune system than other form of estrogens, such as estradiol. Vaginal estriol does not increased the risk for heart disease, stroke, or cancer. (Rahn et al., 2014) In summary, patients with RRMS may significantly benefit from estriol as an adjunctive therapy to MS, improving quality of life and restoring myelin

HYPOTHESIS:

Transvaginal estriol offers a safe adjunctive therapy for female MS patients, it improves urogenital symptoms as well as promotes remyelination.

METHODS:

Subjects: Patients with relapsing remitting MS and urogenital symptoms (frequency, urgency, frequent urinary tract infections, incontinence) will be invited to participate in the study. Enrollment will be during their scheduled clinic appointment. Patients will be screened by a member of the study team during their visits to see if they qualify, if so they will be invited to participate in the study.

The clinical trial will be explained to potential participants in detail, reviewing the objectives and methodology of the study. There will be adequate time allotted to answer any questions or concerns from the potential participants. Those patients interested in participating in the study will be asked to sign the consent form. In order to remind patients about their follow-up visits, lab work, etc., they will be contacted routinely. Participants will be instructed to call in case of questions or concerns. Patients will be evaluated clinically during their scheduled follow up. Patients will be instructed by the primary investigator how to correctly use the vaginal cream. This will be done at their enrolment and reinforced by the principal investigator, during their follow up visits.

Inclusion criteria:

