- 1. Female patients with RRMS between the ages of 35 to 65.
 - A) Being prescribed vaginal estriol to treat their urogenital symptoms.
 - B) Patients that had underwent menopause or surgical hysterectomy.
- 2. Patients will continue their disease modifying agent for MS during the trial.

Exclusion criteria:

- 1. Patients with personal history of breast cancer, uterine or ovarian cancer.
- 2. Patients with history of fibrocystic breast disease, heart attack or stroke.
- 3. Patients with history of thromboembolism.
- 4. Patients with progressive multiple sclerosis
- 5. Patients who are unable to undergo an MRI
- 6. Males
- 7. Patient is already on vaginal or oral or transdermal estrogens
- 8. Pregnant or breast-feeding patients
- 9. Patient taking sex hormones eg testosterone for libido
- 10. Patients taking DHEA or OTC related products that could influence the hormonal milieu.
- 11. Patient with prolapse uterus or conditions that would impact on transvaginal absorption of estriol

Enrollment in the study will be timed to their follow up brain MRI which will be performed as standard of care. Patients that have no baseline MRI or are unable to undergo MRI will be excluded from the study.

Site of study: The TTUHSC department of Neurology, MS clinic, Lubbock, TX; The TTUHSC Department of Ophthalmology and Visual Sciences, Lubbock, TX

Design:

This is a single-group prospective repeated-measures pilot trial. Duration is 12 months

Intervention:

Estriol vaginal cream will be formulated by Twin Oaks Pharmacy's compounding pharmacy, Regional Pharmacy, by the same compound specialist. 30 mg estriol powder will be mixed with 5 mL of propylene glycol and 22 g of vaginal base cream. The product can be stored at room temperature and has a shelf life of up to 4 months. It comes with an applicator.

The 1 mg dosing was chosen due to evidence in previous trials, and a systematic review of randomized trials comparing vaginal estrogens. It was concluded that the 1mg vaginal estroid, was superior to lower doses for the treatment of urogenital symptoms. (Rahn et al., 2014).

Study visits/Roles of subjects:

Initial visit:

After the informed consent has been obtained and all questions have been addressed Potential participants will be screened to ensure they are eligible for the clinical trial. Once eligibility has

been verified

- 1. Blood will be collected for baseline laboratory studies serum estriol, FSH and LH level. (about 20 ml of blood)

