- 2. Baseline urogenital status will be evaluated by
 - Bladder Control Scale (BLCS) questionnaire
- 3. Multiple Sclerosis Quality of Life-54 (l-54) questionnaire will be completed
- 4. Baseline Visual Evoked Potential (VEP) within 4 weeks of Initial Visit
- 5. Optical Coherence Tomography (OCT) (occurs at the Ophthalmology clinic) within 4 weeks of Initial Visit
- 3 Tesla brain MRI will be performed as well. (within 3 months of initial visit)
- Dispense vaginal estriol cream once all baselines are complete

The primary investigators will instruct how to correctly use vaginal cream. Patients will be instructed to draw 1 mg of estriol vaginal cream with the applicator and apply intravaginally. They will be instructed to lay on their back for 30 min after vaginal cream application once a day for the duration of the study. The applicator is reusable, cleaning technique will also be given to the patient during their visit and reinforced during follow up. The applicator will be washed with regular soap and water and let air dry.

Patients will be instructed not to start applying vaginal cream until baseline lab work and imaging has been performed.

Three-month visit (90 days +/- 10 days):

- BLCS questionnaire will be completed
- Blood will be collected for serum estriol, FSH and LH level. (about 20 ml of blood)
- VEP and OCT will be also performed. ± 3 weeks of 3 month Visit
- Dispense vaginal estriol cream

Six-month visit (180 days +/- 10 days):

- BLCS questionnaire will be completed
- Blood will be collected for serum estriol, FSH and LH level. (about 20 ml of blood)
- VEP and OCT will be also performed. ±-3 weeks of 6 month Visit
- Dispense vaginal estriol cream

Nine-month visit (270 days +/- 10 days-FINAL VISIT):

- BLCS and MSQOL-54 questionnaires will be completed
- Blood will be collected f serum estriol, FSH and LH level. (about 20 ml of blood)
- 3 Tesla brain MRI will be repeated. \pm 3 months of 9 month Visit

During each visit patients will be questioned for adverse events, patients will also have a number to call in case of questions, concerns or adverse events.

Due to the nature of RRMS there might be acute exacerbations in which the patient will be treated with IV methylprednisolone 1gm a day x 3 to 5 days, this is the standard of care for MS exacerbations.

Schedule of events

Procedures	Screening visit	3 month visit	6 month visit	9 month visit FINAL VISIT
Date				
ICF	Х			
1&E	Х			
Blood work	x	x	x	x
BLCS	x	x	x	x
questionnaire				

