• Optical coherence tomography (OCT) (noninvasive scan of the retinal layer which provides morphology imagery of the ganglion cell layer which is frequently affected in MS) (Noninvasive test, duration of about 5 to 10 min to perform, patient has to stay still and focus on a small light while we take a picture of the retina layer with the device.)

Data Sheet: A spreadsheet is attached. We will be gathering demographic data, MRI information, EDSS score, and electrophysiologic information, for details please see the spreadsheet attached.

Outcome variables:

1- Urogenital symptoms such as frequency, incontinence, frequent urinary tract infections, and BLCS questionnaire scores.

2- Remyelination (measured by brain MRI 3 DTI, other measurements include presence of T2 lesions, Flair lesions, DWI, T1 black hole, and DTI; Optical coherence tomography (OCT); and visual evoked potentials (VEP).

3- Quality of life, assessed using MSQOL-54 questionnaire.

Analysis:

Patient characteristics will be summarized using frequency (percentage) for categorical variables, and mean (SD) or median (interquartile range) for numerical variables as appropriate. Changes in blood work variables during the course of the study will be assessed using one-way repeated-measures analysis of variance (ANOVA). Compliance assessments will be used as covariate to adjust the differences if necessary, using an analysis of covariance model (ANCOVA). Urinary symptoms, and quality of life data will be analyzed using mixed-effects linear or logistic regression models for continuous or binary outcomes respectively. These models will account for the effect of estriol over time, compliance with treatment, and relevant patient characteristics.

Justification for Sample size:

This is a pilot study. We are planning to include 20 patients. Each patient will be their own control in a single-group repeated measures design. Assuming a significance level $\alpha = 0.05$, and power 1- $\beta = 0.80$, a

TEXAS TECH UNIVERSITY HEALTH SCIENCES CENTER IRB NUMBER: L19-020 IRB APPROVAL DATE: 12/13/2019

sensitivity power analysis determined that a moderate effect size (d=0.53 to d=0.66) would be required to detect statistically significant changes in the main outcome.

Risks

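### Nothing stops the single baseline BLCS and MSQOL-54 from being scored during a urinary tract infection, so with no control group any excess of infection at baseline over follow-up would read as an estriol benefit

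*Combined protocol and SAP*

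**What the plan says.** The Subjects paragraph under METHODS has women approached because of urinary symptoms, and repeated infection is one of those it lists: "Patients with relapsing remitting MS and urogenital symptoms (frequency, urgency, frequent urinary tract infections, incontinence) will be invited to participate in the study". The timing follows the clinic calendar: "Enrollment will be during their scheduled clinic appointment". The Inclusion criteria section adds that enrolment is tied to a routine follow-up brain MRI.

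The one symptom-related inclusion criterion is "Being prescribed vaginal estriol to treat their urogenital symptoms". The exclusion list has 11 items and ends with "Patient with prolapse uterus or conditions that would impact on transvaginal absorption of estriol". None of them concerns a current or recent urinary infection.

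At the initial visit, "Blood will be collected for baseline laboratory studies serum estriol, FSH and LH level"; no urine test is listed. The next step begins "Baseline urogenital status will be evaluated by" and names one instrument, the BLCS. MSQOL-54 is also completed once before treatment. The cream is handed over only when all baselines are done. VEP and OCT may take up to 4 weeks and the MRI window is 3 months. No step repeats or postpones either questionnaire. BLCS is repeated at months 3, 6 and 9, and MSQOL-54 only at month 9.

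The Justification for Sample size section gives the comparator: "Each patient will be their own control in a single-group repeated measures design". The Analysis section plans mixed-effects models with the effect of estriol over time, compliance and relevant patient characteristics. It names no term for infection.

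**The concern.** Frequency, urgency and incontinence are reasons for invitation, and an acute infection can produce all three. A woman assessed during one could have a BLCS score above her usual level. Because the cream waits for the other baselines, the infection may clear before her first dose while the raised score stays as her reference. That part of her improvement cannot be due to estriol.

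MSQOL-54 could be affected in the same way. The background section on urinary issues describes "urinary tract infections which can have a direct impact on MS, worsening neurologic symptoms", so a lower quality-of-life score during infection is plausible, although the protocol does not say so of this questionnaire.

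A randomised comparison would share such fluctuation between arms. Here there is nothing to subtract it from, and with 20 women a few distorted baselines carry weight. The issue is the state of the patient when the questionnaire is scored. How infections are counted as an outcome is a separate matter.

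**Working it through.** **The plan's own figure.** The Justification for Sample size section gives a detectable effect of d = 0.53 to 0.66 for 20 patients, alpha 0.05 and power 0.80. A two-sided paired t-test with n = 20 reaches power 0.80 at d = 0.66, the upper end. The lower end is reproduced approximately (0.54) by a repeated-measures ANOVA with four measurements, if the correlation is assumed to be 0.5, which the plan does not state. These figures only give a scale for the bias.

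**Inputs from the documents.** n = 20, alpha = 0.05, BLCS range 0 to 22 with higher scores worse, one baseline score.

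**Assumed inputs, because the documents give none.** SD of change without infection 4 points, BLCS raised by h = 6 points during an infection, no true estriol effect, one baseline compared with one follow-up visit, two-sided paired t-test.

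**Formula.** With p_b the share infected at the baseline score and p_f the share infected at the follow-up score, the spurious mean improvement is h × (p_b − p_f). Only the difference in shares produces bias. The false-improvement rate is the simulated share of trials with t above t(0.975, 19).

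| Infected at baseline | Infected at follow-up | Spurious mean improvement | False-improvement rate |
|---|---|---|---|
| 0% | 0% | 0 | 2.5% |
| 15% | 15% | 6 × 0 = 0 | about 2.5% |
| 20% | 20% | 6 × 0 = 0 | about 2.5% |
| 15% | 5% | 6 × 0.10 = 0.6 point | about 7% |
| 0% | 15% | 6 × (−0.15) = −0.9 point | below 2.5% |

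In the fourth row the shift is 0.6 / 4 = 0.15 SD, against a detectable effect of 0.66 × 4 = 2.64 points at the plan's upper figure.

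**If nobody is infected at follow-up.** One woman scored 6 points too high shifts the mean by 6 / 20 = 0.3 point and gives about 4%. Three such women shift it by 18 / 20 = 0.9 point and give about 10%. These are upper cases, because women recruited partly for repeated infections can also be infected at month 3, 6 or 9.

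**What the last table row means for the remedy.** Clearing infection from baseline alone, with 15% still infected at follow-up, would bias the comparison against estriol by 0.9 point. A rule has to apply to both ends.

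**The case against.** A reader might infer that the plan selects women when infection is at its worst, so that ordinary recovery will be counted as an estriol effect and the bias runs only towards benefit. The documents do not support that.

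- Entry is at a scheduled appointment timed to a routine MRI. It is not triggered by a flare.
- Repeated infection as an invitation symptom describes a pattern. It does not mean infection on the day.
- The criterion "Being prescribed vaginal estriol to treat their urogenital symptoms" means that a prescriber has already judged estriol suitable for the symptoms. That is a filter, though not a required check for infection.
- Infections at follow-up push the other way, and equal rates cancel.

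All of this stands, and it limits the point to a possibility of unknown size. Some excess at baseline remains plausible, because entry depends on current urinary symptoms and the follow-up visits do not.

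Three further points are fair. The BLCS form and the data sheet are attachments that are not shown, so the recall period of the scale and any infection field are unknown. The planned analysis is a mixed model over four time points, so the paired t-test above is only a guide. And the trial is openly a single-group pilot, with many sources of fluctuation that it cannot separate. None of these puts a rule on infection at scoring into the protocol text, and this source is cheap to record.

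**Conclusion.** The gap is real: neither the eligibility criteria nor the initial-visit steps prevent either baseline questionnaire from being scored during a symptomatic infection, and the design cannot separate recovery from treatment. The bias depends on an excess of infection at baseline over follow-up, and the documents show neither that excess nor its size. Under the assumed SD of 4 points and rise of 6 points, 15% against 5% takes the false-improvement rate from 2.5% to about 7%; equal rates leave it at about 2.5% and only add noise. An excess at baseline could also partly reflect real prevention of infection by estriol, which this design cannot tell apart from recovery. The point merits a short amendment. It does not by itself invalidate the trial.

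**What to change.** 1. At every BLCS or MSQOL-54 visit, baseline included, record from history and the clinic record whether the woman has a current or just-treated urinary infection, and the date of the last one. No new test is needed.
2. If she has one, complete the questionnaire later: at baseline within the existing baseline period and before the first dose, at follow-up within the visit window (±10 days). Where that is not possible, complete it and flag the score.
3. Repeat the BLCS and MSQOL-54 models without flagged scores, with the same rule at baseline and follow-up.
4. Keep infections as their own outcome in all women, so that any effect of estriol on infection is not lost when flagged scores are set aside.

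The investigators should define the infection-free interval in advance. This concerns only when questionnaires are scored; no rule on starting treatment or managing infection is proposed. If enrolment has finished, infection status and dates may still be recoverable from clinic records for the sensitivity analysis.

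The cost is a short amendment, one or two added data fields, a short delay in questionnaires for a few women, and one extra sensitivity analysis. With a ±10-day window some follow-up scores will be flagged instead of deferred.

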MSQOL-54	x			x
questionnaire				
VEP (4 week	x	x	x	
window for				
screening visit or 3				
week window for 3				
and 6 month visits)				
OCT (4 week	x	x	x	
window for				
screening visit or 3				
week window for 3				
and 6 month visits))				
MRI variables (3	x			X
month window)				
Vaginal cream	x			
instructions				
Vaginal cream	х	x	x	
dispensing (once				
baselines				
complete)				
Compliance of		x	x	x
vaginal cream use				

Materials, instruments or measurements:

Urogenital measurements:

- Bladder control scale (BLCS) questionnaire (validated and used for evaluation of MS bladder symptoms. {Turnbull et al, 1992}). Raw scores on the 4 items are summed to create a Bladder Control Scale (BLCS) total score. Scores can range from 0-22, with higher scores indicating greater bladder control problems. See attached document. TEXAS TECH UNIVERSITY HEALTH SCIENCES CENTER

Quality of life:

- Quality of life questionnaire (Multple Sclerosis Quality of Life-54 {MSQOL-54}. Validated and widely used for MS patients. (Vickrey et al, 1995) (Vickrey et al, 1997). The questionnaire includes 54 questions that provide scores on physical and mental health status. Both scores can range 0-100. See attached document.

Blood work:

Levels of estriol, FSH, LH will be performed in Texas Tech Health Science Laboratory ([name] certified lab). The assay used will be the Beckman Coulter Access 2 immunoassay system analyzer. This will be run by an established OB/GYN hormone laboratory under the supervision of [name] and [name].

Re-myelinating measurements:

• Visual evoked potential (VEP) (measurement of the electrical signal recorded at the scalp over the occipital cortex in response to light stimulus) VEP/Prolongation of the P100 latency, is an indirect tool for remyelination in MS. (The test is non-invasive, patients will be looking at a checkboard pattern while the technician is measuring the time it takes to register the image to the brain cortex. This is achieved with scalp electrode in the posterior region.)

• 3Tesla brain MRI (performed as standard of care with no extra cost) will be evaluated for possible changes in white matter lesions, and Diffusion Tensor Imaging (DTI). This will be read by an expert MD collaborator independent from primary investigator.

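### Time from the last application to the 3-, 6- and 9-month blood draws is neither fixed nor visibly recorded, so differences in serum estriol among on-treatment visits mix sampling time with exposure

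*Combined protocol and SAP*

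**What the plan says.** All references are to the combined protocol and SAP.

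- **Application.** Under Initial visit, patients are told to use the cream daily: "vaginal cream application once a day for the duration of the study". No time of day is given.
- **Sampling.** Under the Three-month and Six-month visits: "Blood will be collected for serum estriol, FSH and LH level. (about 20 ml of blood". The Nine-month visit repeats this in nearly the same words. The only timing rule is the visit window, for example "Three-month visit (90 days +/- 10 days", with the same 10-day tolerance at 6 and 9 months. It is counted in days from start, not hours from application.
- **Schedule of events.** There are rows for blood work, cream dispensing and compliance. None is for the time of the last application or of the draw.
- **Baseline.** It is untreated: "Patients will be instructed not to start applying vaginal cream until baseline lab work and imaging has been performed". Exclusion criterion 7 removes outside estrogen at entry: "Patient is already on vaginal or oral or transdermal estrogens". Criteria 9 and 10 do the same for sex hormones and DHEA-type products.
- **Assay.** The Blood work section says "The assay used will be the Beckman Coulter Access 2 immunoassay system analyzer". No quantification limit is stated.
- **Analysis.** "Changes in blood work variables during the course of the study will be assessed using one-way repeated-measures analysis of variance (ANOVA"). Compliance is the only covariate named for this analysis, and only if needed.
- **Outcome variables.** Urogenital symptoms, remyelination measures and quality of life are listed. Blood work is not.

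**The concern.** With once-daily use, a serum level may depend on how long ago the cream was applied as well as on how much reaches the circulation. A fully compliant patient could be sampled 2 h after application at one visit and close to 24 h after at the next. The planned ANOVA would treat the two values as like for like. The compliance covariate does not help, because it does not measure hours since application.

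Aim 2 looks for a brain effect of a vaginal product. The background relies on the cream being well absorbed, and exclusion criterion 11 removes conditions that would impair absorption. Serum estriol is the plan's only direct measure of that step. If its on-treatment values are hard to read, a positive or null remyelination result in 20 patients is harder to explain, and a later study has less to build on. An application time that was not written down cannot be reliably recovered afterwards.

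**Working it through.** **The plan's own figure.** There is none for serum estriol. The effect size under Justification for Sample size (d = 0.53 to 0.66) concerns the main outcome. Its upper end reproduces as a two-sided paired t-test with n = 20 (d = 0.660). Its lower end is close to a four-visit repeated-measures ANOVA with an assumed correlation of 0.5 (d = 0.54). Nothing below depends on it.

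**Inputs.** From the documents: once-daily application, draws at 3, 6 and 9 months, and no rule on hours since application. Assumed, because the documents give no kinetic data:
- first-order decline with a half-life h of 3, 6 or 12 h
- time since application spread evenly over a width w of 22 h (2 to 24 h) or 8 h
- within-patient log SD s, apart from timing, of 0.4 or 0.6

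**Step 1: level ratio between two draws at unchanged exposure.** Ratio = 2^(gap/h).
- Draws at 2 h and 24 h (gap 22 h): 161, 13 and 3.6 for h = 3, 6 and 12.
- Draws at 10 h and 18 h (gap 8 h): 6.3, 2.5 and 1.6.

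**Step 2: log-scale SD from timing alone.** Log level falls by ln 2/h per hour, so timing SD = (ln 2/h) × w/√12. Here 22/√12 = 6.35 h and 8/√12 = 2.31 h.

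**Step 3: variance inflation.** Factor = (s² + timing SD²)/s².

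| Spread | h | Timing SD | Factor, s = 0.4 | Factor, s = 0.6 |
|---|---|---|---|---|
| 22 h | 3 | 1.47 | 14.46 | 6.98 |
| 22 h | 6 | 0.73 | 4.36 | 2.50 |
| 22 h | 12 | 0.37 | 1.84 | 1.37 |
| 8 h | 3 | 0.53 | 2.78 | 1.79 |
| 8 h | 6 | 0.27 | 1.44 | 1.20 |
| 8 h | 12 | 0.13 | 1.11 | 1.05 |

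**Step 4: what a common window buys.** For an illustrative 2-h window, 2/√12 = 0.58 h. The timing SD is then 0.13, 0.07 and 0.03, and the factor is at most 1 + 0.13²/0.4² = 1.11.

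**Step 5: cross-check with a different model.** A steady-state one-compartment profile was simulated with an assumed absorption half-life of 0.5 to 1 h and draws at any time in 0 to 24 h. Two draws at unchanged exposure differ at least 2-fold in about 81–83% of pairs (half-life 2 h), 65–68% (4 h), 38–42% (8 h), 18–21% (12 h) and 0% (24 h). Draws kept to 11–13 h after application bring this to 0% throughout. The problem is large at short half-lives and small near 24 h.

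**Step 6: can a rise from baseline still be seen?** In the same simulations, with n = 20, near-zero untreated levels, an assay able to read the values, half-lives of 2 to 12 h and random timing, the rise was detected in at least 95% of trials. At a 2-h half-life (absorption half-life 1 h), however, about 56% of random draws lay below 10% of peak, so a high assay limit could hide uptake.

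**The case against.** A reader might infer that serum estriol cannot show systemic uptake at all. The documents do not support that. The first sample precedes any cream, outside estrogens are excluded at entry, and blood is drawn at all four visits, so a clear rise would show some uptake at whatever hour the draw fell. Step 6 agrees.

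A reader might also take serum estriol to be the only objective check on compliance. That fails too: Monitoring lists drug accountability among the records open to inspection, and the Schedule of events has a compliance check at 3, 6 and 9 months.

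Three further objections have weight.

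- The data sheet is attached but not shown, and the investigator's instructions on use are not reproduced. It cannot be said that patients choose their own time, or that no time field exists. The defensible statement is that the visible text contains neither a sampling rule nor a time field, and that the analysis uses no such time.
- A 22-h spread within one patient is extreme for daytime visits and a daily routine, and each patient is her own control. The 8-h rows are an equally assumed but milder case, with factors of 1.05 to 2.78.
- Timing that varies at random adds noise to the mean change. It biases that change only if the hour shifts systematically from visit to visit.

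These narrow the point and leave its core standing: the on-treatment values cannot be compared cleanly with one another.

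**Conclusion.** The concern holds in limited form. Even if the plan is followed exactly, nothing in the visible text keeps differences among the 3-, 6- and 9-month estriol levels from mixing sampling time with exposure. A clear rise from baseline remains evidence of some uptake. What becomes hard to interpret is the size of that uptake, any trend across visits, and a null result, which a late draw or an unstated assay limit could produce.

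The variance inflation runs from about 1.05 to about 14. The half-life, the spread of draw times and the within-patient SD are all assumptions, so this is a range of possibilities and not an estimate.

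The listed outcomes are not affected. Serum estriol is not among them, no uptake objective is stated, and no Aim 2 analysis is conditional on serum level. This is a cheap improvement in interpretability, not a threat to the trial's main results.

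**What to change.** 1. Record the date and clock time of the last application and of the blood draw at 3, 6 and 9 months. If the data sheet already has these fields, refer to them in the visit lists and the Schedule of events.
2. Book each patient's three on-treatment draws in the same post-application window. The application schedule itself is not touched.
3. Keep the baseline-to-visit comparison, as a paired change or an all-visit model, because it is the one that shows uptake. State the assay's quantification limit and a rule for values below it, since untreated levels may fall there and a log cannot be taken of zero.
4. Add a separate mixed model of log estriol at 3, 6 and 9 months with hours since application as covariate. It must be separate because that covariate has no value at baseline.

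The cost is two form fields, a reminder when visits are booked, and slightly less flexible appointment times. No extra blood or procedure is needed.
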